## 12 Sample size determination

In this trial, propranolol was used as the control group to evaluate the efficacy and safety of the atenolol group (experimental group). The treatment response after 6 months of medication was used as the key therapeutic index. To calculate the sample size for this trial, we used the following assumptions:

- (1) A 2-sided 0.05 significance level;
- (2) Ratio of the propranolol group: atenolol group = 1:1;
- (3) A statistical power of 90%;
- (4) A 20% dropout rate due to ineligibility;
- (5) A follow-up of at least 96 weeks;
- (6) A 24-month recruitment period; and
- (7) In this trial, the atenolol group's evaluation variables were compared with the propranolol group's evaluation variables to test for noninferiority. The hypotheses are listed below:

-H0: Twenty-four weeks after therapy initiation, compared to the treatment response of propranolol therapy, that of atenolol was inferior; and

-H1: Twenty-four weeks after therapy initiation, compared to the treatment response of propranolol therapy, that of atenolol was non-inferior.

(8) Very limited data are available in the literature that can be used to set hypotheses for atenolol treatment. Existing case studies are mainly based on small single-center experiences. According to previous studies, propranolol's total treatment response is assumed to be 70-100%, and atenolol's total treatment response is assumed to be 70-100%. In addition, assuming that the atenolol on propranolol response rate does not fall by greater than 15%, the noninferiority margin was selected to be -15%.

(9) Assuming the ulceration rate in both groups to be 10%.

(10) A sample size of 180 patients was determined to be required for each group (a total of 360 patients).

[figure not shown]
[figure not shown]
---

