## 19 Primary outcome measures

The primary outcome measure was the clinical response at 6 months in the intention-to-treat population. The intention-to-treat population was defined as all patients who had undergone randomization. If after assignment, a patient did not receive a drug administration or if an evaluation was never made after drug administration, the patient was excluded from the intention-to-treat population.

Digital photographs of IHs were independently obtained by three investigators who were unknown to the study group assignment. In the case of multiple IHs, only the most clinically important IH (typically the largest or most ulcerated IH) was documented.

Changes in IH size and color were classified as a complete response, nearly complete response, partial response or no response. The primary outcome measure was any response or nonresponse at 6 months in the intention-to-treat population of all patients who underwent randomization. The any response included compete, nearly complete and good responses; the nonresponse included stable or deteriorated:

-A complete response was defined as no redundant tissue or telangiectasia was identified.

-A nearly complete response was defined as a minimal degree of telangiectasis, erythema and skin thickening.

-A partial response was defined as a size reduction or change in color that did not meet the nearly complete resolution criteria.

-Stable was defined as no changes in size or color between baseline and month 6.

-Deterioration was defined as further growth of the target hemangioma.

Treatment failure was defined as patients withdrawing from trial treatment due to nonresponse and/or severe adverse events.

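### Does 180 per arm miss the planned 90% power, given that response is stated only as a 70-100% range?

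*Combined protocol and SAP*

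**What the plan says.** Section 12 introduces its list with "To calculate the sample size for this trial, we used the following assumptions". The items that bear on power are:

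- "A 2-sided 0.05 significance level", 1:1 allocation and 90% power;
- "A 20% dropout rate due to ineligibility";
- a noninferiority comparison of atenolol with propranolol on response at 24 weeks, with a margin of -15%;
- for the control arm, "propranolol's total treatment response is assumed to be 70-100" percent, and for the experimental arm, "atenolol's total treatment response is assumed to be 70-100" percent. Both ranges are attributed to earlier studies, after a remark that data on atenolol are scarce.

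The section ends: "A sample size of 180 patients was determined to be required for each group", 360 in all. Two figures follow that statement and could not be read in the text available for this check.

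Two other sections affect how many patients are analysed. Section 19 removes from the intention-to-treat population anyone never dosed, and adds that "if an evaluation was never made after drug administration, the patient was excluded from the intention-to-treat population". Section 25.3 includes everyone who took at least one dose and handles missing outcomes by best-case and worst-case scenarios.

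**The concern.** A noninferiority sample size for two proportions needs one assumed rate per arm and an assumed true difference. The readable text of Section 12 gives a 30-point range for each arm and no true difference. It also does not say whether 180 is before or after the dropout allowance. The variance of a proportion falls as the rate rises from 70% towards 100%, so power differs greatly between the two ends of that range. A reader who takes 90% to hold throughout would be misled at the low end.

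At stake is the chance that the trial fails to show noninferiority when the drugs are truly equal. Stated power of 90% implies 1 in 10. At a common 70% response it would be about 1 in 5 with the full 20% lost from the analysis, or about 1 in 8 with nobody lost.

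**Working it through.** **Inputs from Section 12.** Margin 0.15, read as an absolute difference; two-sided 0.05, applied as one-sided 0.025 (z = 1.960); 90% power (z = 1.2816); 1:1 allocation; 180 per arm; 20% dropout, leaving 180 x 0.8 = 144.

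**Assumption not in the readable text.** Equal true rates in the two arms, unless stated otherwise.

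**Can 180 be reproduced?** With pC for propranolol and pT for atenolol,

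n per arm = (1.960 + 1.2816)^2 x [pC(1-pC) + pT(1-pT)] / (0.15 + pT - pC)^2.

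| True rates | n evaluable per arm | Route to the randomized number |
|---|---|---|
| 81% in both | 143.7, so 144 | 144 / 0.8 = 180 |
| 80% in both | 149.4, so 150 | 150 x 1.2 = 180 (150 / 0.8 would give 188) |
| 74% in both | 179.7, so 180 | 180 with no inflation |
| 72% propranolol, 74% atenolol | 143.2, so 144 | 144 / 0.8 = 180 |
| 70% in both | 196.1, so 197 | 197 / 0.8 = 247 |

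Several planning points inside 70-100% give 180. The text does not identify which one was used, and 70% in both arms is not among them.

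**Power delivered by 180 per arm.** With a common rate p and n analysed per arm,

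power = Phi(0.15 / sqrt(2p(1-p)/n) - 1.960).

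Worked at p = 0.70:

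- n = 144: sqrt(0.42/144) = 0.0540; 0.15/0.0540 = 2.777; 2.777 - 1.960 = 0.817; power 79.3%.
- n = 180: sqrt(0.42/180) = 0.0483; 0.15/0.0483 = 3.105; 3.105 - 1.960 = 1.145; power 87.4%.

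| Common rate | 144 analysed | 180 analysed |
|---|---|---|
| 70% | 79.3% | 87.4% |
| 75% | 83.6% | 90.8% |
| 80% | 88.9% | 94.5% |
| 81% | 90.05% | 95.2% |
| 85% | 94.6% | 97.9% |
| 90% | 98.9% | 99.7% |

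Solving for 90% power gives a common rate of 81.0% with 144 analysed and 73.9% with 180. Exact binomial enumeration at 70% agrees: about 80% with 144, and 87.4% (Wald) to 88.0% (Newcombe) with 180.

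**How much of the range is affected.** With 144 analysed, (81 - 70)/30 is a little over a third. With 180 analysed, (73.9 - 70)/30 is about an eighth.

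**Sensitivity to the assumptions.**

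- *True deficit for atenolol.* At 81% against 79%, power is 79% (144) or 87% (180). At 90% against 85%, it is 73% or 82%.
- *One-sided 0.05, which the plan does not state.* Power at a common 70% would be 87% (144) or 93% (180).
- *Dropouts kept as nonresponders in both arms, a rule the plan does not set for its main analysis.* A true 81% becomes 0.8 x 81% = 64.8%, and power with 180 is 85%.

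**The case for a change.** The strongest case for a change is that the shortfall at 70% does not depend on the missing figures. It follows from the listed margin, significance level, range and sample size, and it remains at 87% even with no dropout. Section 12 itself says that evidence on atenolol is thin, so a low rate cannot be ruled out. Equal rates are also the favourable case compared with any true deficit for atenolol. The remedy would be cheap: name the planning rates and the dropout handling, and add a line of power values, with no extra patients.

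The arithmetic in that case stands. The inference that the plan is deficient does not, for four reasons.

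1. A sample size is computed at a point, and every trial has less than nominal power at less favourable values. Section 12 reports the range as what earlier studies found; it does not claim 90% throughout. At the midpoint, 85%, power is about 95% even with the full 20% lost.
2. The low end is not the natural planning point for this endpoint. Section 19 counts any reduction in size or change in color as at least a partial response, which is a lenient threshold.
3. The 79% figure needs all 20% to leave the analysis. The allowance is tied to ineligibility. Section 19 removes only patients never dosed or never evaluated, so a child seen at week 1 and then lost is not removed by that rule. The number analysed could lie anywhere between 144 and 180.
4. A failed noninferiority test is interpreted from the confidence interval for the difference set against -15 points. That interval already reflects the observed rates and the number analysed. Power recomputed at the observed rate would add nothing to it.

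**Conclusion.** No change to the plan is needed. The figure of 180 per arm agrees with planning rates inside the stated range and is not an arithmetic error. With equal true rates, an absolute 15-point margin and one-sided 0.025, it gives 90% power from a common response of about 74% if all 180 are analysed, or about 81% if 20% are lost. At 70% the power is 87% or 79%. These figures assume that patients lost leave the analysis rather than being counted as nonresponders.

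What remains is that the readable text does not name the planning rate or say how the 20% entered the calculation. The figures closing Section 12 may supply both. If they do not, a sentence there would help readers, but that is optional reporting: the 360 patients, the margin, the analysis and the decision rule would all stay as they are.

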**13 Enrollment/Randomization:**

Before enrollment, the parents or guardians could decide if they wanted to be included the study. Each eligible subject whose parent or guardian provided informed consent for either drug was assigned a unique subject number. Randomization was 1:1 according to computer-generated randomization sequences with blocks in random order. Statistical Analysis Software was used to produce random numbers, and there was no stratification factor in this study.

The West China Hospital of Sichuan University is the central investigative site (CIS). The CIS generated a randomization list and implemented randomization using an interactive web-based system. The CIS was in charge of randomization data management and application. In addition, randomization information was independently managed, and access was limited for investigators who treated the patients. Two randomized sequences were used for each center so that enrollment could be stratified by exposure to either propranolol or atenolol. Subjects who were randomized to a treatment had their subject number linked to a corresponding drug kit.

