**Protocol outline**

|                               |   |
|-------------------------------|---|
| Title                         | Propranolol versus atenolol for problematic infantile hemangiomas: a randomized clinical trial  |
| Version date                  | July 1, 2017  |
| Research Institutions         | Six separate investigation sties in China   |
| Principle Investigators       | [name], [name]  |
| Purpose                       | Comparing the efficacy and safety of propranolol versus atenolol in patients with problematic infantile hemangiomas.  |
| Design                        | A prospective, multicenter, randomized, controlled, open-label clinical trial.  |
| Subjects                      | Patients with superficial or mixed infantile hemangiomas who require systemic therapy.  |
| Research Duration             | Four years  |
| Methods                       | 
Participants are randomized to receive either propranolol or atenolol for at least 6 months.
 
Participants complete a baseline survey and a survey at 96 weeks of follow-up.
 
The primary outcome measure is the clinical response at week 24.
 
Secondary outcome measures include Hemangioma Activity Score, successful initial response, complete ulceration healing time, quality of life, rebound rate, and response at week 96.
 
Frequency and severity of adverse events will be recorded.
 |
| Expected results and meanings | Evidence supporting the use of atenolol as a first-line treatment of choice in infantile hemangioma.  |

---

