### 25.3 Primary outcome analysis

Based on the intention-to-treat principle, the primary outcome analysis was performed in the intention-to-treat population. All patients treated with at least one dose of study medication (propranolol or atenolol) were included and analyzed in the group to which they were randomized.

Primary outcomes were analyzed by sensitivity analysis. Best-case (response) and worse-case (nonresponse) scenarios were evaluated based on the intention-to-treat principle (in the best-case scenario, missing data in the propranolol group were considered failures, and missing data in the atenolol group were considered successes). In addition, missing data in the propranolol group were considered successes, and missing data in the atenolol group were considered failures.

In addition, a per protocol analysis was performed. This means that only patients without major protocol violations are included. These patients fulfilled all inclusion and exclusion criteria and carried out all medical procedures/visits according to the protocol.

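### Section 13 denies stratification yet describes sequences for each center, and no analysis section mentions center; if allocation was by center, an unadjusted interval would be slightly too wide

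*Combined protocol and SAP*

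**What the plan says.** Section 13 (Enrollment/Randomization) makes four statements about allocation:

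- Allocation was 1:1 from "computer-generated randomization sequences with blocks in random order". Block sizes are not given.
- On stratification: "there was no stratification factor in this study".
- On who held the list: "The CIS generated a randomization list and implemented randomization using an interactive web-based system". The list is singular.
- On centers: "Two randomized sequences were used for each center so that enrollment could be stratified by exposure to either propranolol or atenolol".

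The protocol outline gives six sites. The number of infants per site is not stated.

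Section 25.3 (Primary outcome analysis) says that infants are "analyzed in the group to which they were randomized", and sets out missing-data scenarios and a per-protocol analysis. It names no test, estimator or confidence interval for the noninferiority comparison, and no center term. Section 25.4 lists Fisher or chi-square tests with 95% intervals for categorical secondary outcomes, and a generalized linear mixed model for the Hemangioma Activity Score (HAS). The terms of that model are not listed and center is not mentioned.

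**The concern.** The second and fourth statements in Section 13 cannot both be true as written. Separate sequences for each center amount to stratification by center, whatever they are called. The purpose given for them does not work either: exposure to propranolol or atenolol results from randomization, so it cannot be a stratum. A reader cannot tell whether blocks were run within each site or across the whole trial.

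This bears on the analysis. When allocation is balanced within centers and centers differ in response, the differences between centers cancel out of the treatment comparison. An unadjusted standard error still counts them as noise, so its interval is too wide. What is at stake is some lost precision in the noninferiority comparison, and a choice between adjusted and unadjusted analysis that is left open until the results are known.

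**Working it through.** **1. The text.** Of the statements in Section 13, the denial of stratification and the singular list point to one trial-wide sequence. The per-center sentence points to allocation within site. Nothing else in the document decides between them.

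**2. The plan's own sample size.** Section 12 gives a two-sided 0.05 level, 90% power, a 15-point margin, 20% dropout and 180 per group. It gives response only as a range, 70-100%. Assuming 80% in both arms:

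n = (1.960 + 1.282)² × 2 × 0.80 × 0.20 / 0.15² = 149.4, so 150 per arm; 150 × 1.2 = 180.

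This matches the stated figure, but not uniquely: other assumed rates come within 3%. Center plays no part in it. With 20% lost, 180 × 0.8 = 144 per arm remain, so both 144 and 180 are used below.

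**3. Size of the effect if allocation was within center.** Assumptions that the documents do not supply: six equal centers and evenly spaced center response rates. Let m be the mean rate and B the variance of the center rates.

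- Unadjusted standard error: SE_u = √(2 × m(1−m) / n)
- True (and center-stratified) standard error: SE_s = √(2 × [m(1−m) − B] / n)
- Power, unadjusted: Φ((0.15 − 1.96 × SE_u) / SE_s)
- Power, stratified: Φ(0.15 / SE_s − 1.96)

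Rates 65-95%: m = 0.80, m(1−m) = 0.1600, B = (0.15² + 0.09² + 0.03²)/3 = 0.0105, so the within-center variance is 0.1495. At 144 per arm, SE_u = 0.0471 and SE_s = 0.0456.

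Rates 60-98%: m = 0.79, m(1−m) = 0.1659, B = (0.19² + 0.114² + 0.038²)/3 = 0.0168, so the within-center variance is 0.1491. At 144 per arm, SE_u = 0.0480 and SE_s = 0.0455.

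| Center rates (assumed) | Per arm | Power, unadjusted | Power, stratified | Gap (points) |
|---|---|---|---|---|
| 80% everywhere | 144 | 88.9% | 88.9% | 0 |
| 65-95% | 144 | 89.7% | 90.9% | 1.2 |
| 65-95% | 180 | 95.1% | 95.7% | 0.65 |
| 60-98% | 144 | 89.0% | 90.9% | 1.9 |
| 60-98% | 180 | 94.7% | 95.8% | 1.1 |

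**4. Type I error.** Set atenolol 15 points lower in every center.

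- 65-95%: pooled variance sum 0.1600 + 0.2275 = 0.3875; within-center 0.3875 − 2 × 0.0105 = 0.3665. The effective critical value is 1.96 × √(0.3875/0.3665) = 2.015, a one-sided error of 2.2%.
- 60-98%: 0.1659 + 0.2304 = 0.3963; within-center 0.3963 − 2 × 0.0168 = 0.3626. The critical value is 2.049, an error of 2.0%.

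**5. Simulation.** With the same two spreads and allocation within center, simulation gives power losses of about 0.5-1.8 points and unadjusted one-sided error of 2.0-2.4%, close to the formulas. In a separate run (six centers of 60, rates 75-95%), the half-width is 7.35 points unadjusted against 7.21 for a Mantel-Haenszel risk difference. In the widest setting tried there (70-99.9%, six centers of 48) it is 8.21 against 7.87, a gap of about 0.3 points.

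**6. If allocation ignored center.** The unadjusted interval is then correctly sized. Stratifying still raises power by about 0.8-2.8 points when centers differ in these ways, because it removes chance imbalance between centers. With no center differences, the loss from stratifying is at most about 0.6 points.

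**The case against.** The strongest reply is that no mismatch has been shown. If the denial of stratification is the accurate sentence, an unadjusted analysis fits the allocation. Section 25.3 names no interval, so none exists to be wrong. That stands, and it is why the consequence is stated only as conditional.

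A reader might infer three stronger things:

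- *That the plan pools all infants and ignores center.* The sentence in Section 25.3 about analysis by assigned group is an intention-to-treat rule and says nothing about pooling sites. The terms of the HAS model are not listed. The plan is silent on center; it does not exclude it.
- *That the noninferiority conclusion is at risk of being falsely positive.* The error runs the other way: 2.0-2.4% against 2.5%.
- *That blocks were in fact run within each center.* Section 13 does not settle this. Writing it in unverified could put a false statement into the protocol.

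It is also fair to say that the gain is small, that the larger figures come from 144 rather than the planned 180 per arm, and that center spreads of 30-38 points are assumed. Very small centers could make stratification awkward, which is why a pooling rule is needed.

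**Conclusion.** The contradiction in Section 13 and the silence on center in Sections 25.3 and 25.4 are certain and rest on no assumption. The effect on the interval arises only if allocation was by center and response differs between centers. It is then mildly conservative: about 0.5-1.8 points of power and at most about 0.3 points of half-width in the settings examined. Those sizes depend on assumed center rates and center sizes; if centers respond alike, the effect is nil.

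The point merits a correction because the allocation method is a core design fact and because the choice of adjustment is otherwise left open. It does not cast doubt on the validity of the comparison. Center-stratified analysis is sound under either account of the allocation, so that recommendation need not wait for the wording to be settled.

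**What to change.** 1. **Section 13.** Confirm from the randomization system whether blocks were run within center or across the trial. State it once, and remove or correct the sentence about stratifying by drug exposure.
2. **Section 25.3.** Name the primary analysis: a center-stratified risk difference (Mantel-Haenszel or stratified Miettinen-Nurminen) with its 95% confidence interval, compared with the -15 point margin. Fix in advance a rule for pooling small centers. Report the unadjusted estimate as a sensitivity analysis.
3. **Section 25.4.** Include center in the HAS and quality-of-life models, and list the model terms.

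The cost is a few lines of text and a standard estimator. Site should already be on record for every infant, so no new data are needed. The only statistical price is a loss of at most about 0.6 points of power if centers do not differ.

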**14 Trial schedules**

| Contents                                  | Schedule (Study period: 192 weeks)   |    |    |    |     |     |     |     |
|---|--|----|----|----|-----|-----|-----|-----|
|   | 24   | 48 | 72 | 96 | 120 | 144 | 168 | 192 |
| Recruitment of participants               |  |    |    |    |     |     |     |     |
| Primary and secondary outcome measurement |  |    |    |    |     |     |     |     |
| Adverse event measurement                 |  |    |    |    |     |     |     |     |

---

## 15 Pretreatment evaluations

(1) At the initial visit, investigators collected demographic and clinical data. The patients' parents who opted for oral  $\beta$ -blocker therapy provided a thorough medical history (e.g., existence of comorbidities) and family history (e.g., cardiovascular disease).

Acquisition of general information:

- Sex;
- Gestational age;
- Date of birth;
- Age,
- Body weight.

Hemangioma histories were also taken from families, including:

- Age when the hemangioma appeared;
- Changes in the color of the hemangioma; and
- The period during which the hemangioma showed the greatest growth before referral.

(2) In all infants, the following inspections were performed before enrollment:

- Heart rate;
- Blood pressure;
- Blood glucose;
- Full blood count;
- Liver function tests;
- Renal function
- Electrocardiogram (ECG); and
- Echocardiogram.

If cardiovascular abnormalities were detected, the patient were evaluated by pediatric cardiologists to ensure that it would be safe to initiate  $\beta$ -blocker treatment. Echocardiographic findings, such as a false tendon in the left ventricle, a patent ovale, left superior vena cava to the coronary sinus, and small systemic-to-pulmonary arterial collateral vessels, were considered normal variants and are not reported as anomalies.

(3) When patients had more than one IH, detailed information was obtained for the most clinically important hemangioma (typically the largest or most ulcerated lesion). Hemangioma assessments included lesion size, lesion location, stage of growth,

---

morphologic subtypes, depth of involvement, and treatment indication.

(4) According to Chang et al., lesion size was recorded using 'hemispheric' measurement. A soft tape measure was draped over the hemangioma, and the longest diameter and a measurement perpendicular to it were noted to obtain a measurement in cm^2.

(5) Hemangioma lesions were classified by morphologic subtypes:

-Localized: well-defined focal lesions;

-Segmental: a hemangioma involving an anatomic region that was often plaque-like and often measured at >5 cm in diameter; or

-Indeterminate: neither clearly localized nor segmental.

(6) Hemangioma lesions were also be classified by soft-tissue depth:

-Superficial, which was defined as red with little or no evidence of a subcutaneous component;

-Deep, which was defined as blue and located below the skin surface (deep lesions were not considered target hemangiomas in this study); or

-Mixed, which was defined as having both superficial and deep components.

Investigators at all sites received standardized training on hemangioma assessments, including training in measurement techniques and the classification of hemangiomas.

(7) Treatment indications included:

-Disfigurement: Segmental IH; Head or facial IH  $\geq 1.5$  cm; Neck, truck or extremity IH  $\geq 3.0$  cm.

-Causing functional disturbance: Periocular IH with threat to vision, nasal tip and lip ( $\geq 1.5$  cm). If functional concerns were documented, indication for treatment was not classified as disfigurement (facial IH  $\geq 1.5$  cm).

-Ulceration (IH  $\geq 1.5$  cm): ulcerated IH appearing anywhere on the body surface.

-Bleeding (IH  $\geq 1.5$  cm): Bleeding IH appearing anywhere on the body surface.

---

